# SECONDARY OUTCOME MEASURES:

Repetitive Behavior Scale-Revised (RBS-R): The RBS-R is a 44-item self-report questionnaire that is used to measure the breadth or repetitive behavior in children, adolescents and adults with PWS. The RBS-R provides a quantitative, continuous measure of the full spectrum of repetitive behaviors. The RBS-R consists of six subscales including: Stereotyped Behavior, Self-injurious Behavior, Compulsive Behavior, Routine Behavior, Sameness Behavior, and Restricted Behavior that have no overlap of item content. This permits differential identification and scoring of discrete varieties of repetitive behaviors. Participants are asked to read a list of behaviors and choose a score that best describes how much of a problem the behavior has been of the last month. Behaviors are rated on a 4-point scale: 0 - behavior does not occur, 1 - behavior occurs and is a mild problem, 2-behavior occurs and is a moderate problem, 3 - behavior occurs and is a severe problem. On the last question, participants are asked to "lump together" all of the behaviors described in the guestionnaire and provide a rating for how much of a problem these repetitive behaviors are overall on a scale from 1 - 100. 1-Not a problem at all to 100-as bad as you can imagine. The RBS-R measures repetitive behaviors that are specific to PWS symptomatology. It has been used in previous trials of oxytocin in adults with success, as seen in our preliminary data. It is completed by the parents at baseline and weeks 4 and 8 and takes approximately 25 minutes to complete.

**Montefiore-Einstein Rigidity Scale-Revised PWS (MERS-PWS)**: The Montefiore-Einstein Rigidity Scale-Revised (MERS-PWS) is designed to assess three domains of rigid behavior in children and adults with PWS: 1. Behavioral Rigidity (e.g., insistence on sameness, things must be done in his/her way, etc.) 2. Cognitive Rigidity (e.g., special interests, inflexible adherence to rules, etc.) 3. Protest (in response to deviation from rigidity; e.g., verbal objection, tantrum, physical aggression) The MERS-PWS is a clinician-rated scale in that will be completed at baseline, week 4, week 8 and follow up and takes about 20 minutes to complete.

#### Weight, BMI (z-score) and Body Composition via Bioelectrical Impedance Analysis:

Weight and BMI (z-score) will be measured at each visit using a regularly calibrated scale. Body composition, in particular fat mass, will also be measured at each visit using bioelectrical impedance analysis. The Einstein-Mount Sinai Diabetes Research Center regularly completes and advises on the administration of bioelectrical impedance analysis and will provide the necessary equipment and services for this proposal. Both subject weight and body composition

will serve as markers of treatment efficacy as weight and fat loss are expected outcomes of treatment with IN-OXT. Although it is possible oxytocin could modulate energy expenditure, weight and fat loss observed during the 8 week period would be a strong indicator of a decrease in hyperphagia. This should take 15 minutes.

World Health Organization Quality of Life Questionnaire (WHOQOL): The WHOQOL is a guality of life assessment developed by the WHOQOL group with fifteen international field centers in an attempt to develop a quality of life assessment that would be applicable crossculturally. The full-scale assessment WHOQOL-100 comprises 100 questions while the WHOQOL-BREF is a shorter version comprised of 26 items which measure the following broad domains: physical health, psychological health, social relationships and environment which is more convenient for use in large research studies or clinical trials. As seen in our preliminary data, it has proven to have significant change in trials with OXT and will be used to measure quality of life and caregiver burden in this study. PWS has a substantial impact on caregiver burden and quality of life. Thus, it is important to demonstrate that symptom reduction is also clinically meaningful. This scale, completed by parents on a bi- weekly basis, has been validated in other studies, including in PWS. However, WHOQOL is not a PWS- specific assessment. It has been used in multiple disorders including muscular dystrophy, tuberculosis and hypertension. WHOQOL is a parent questionnaire that will be completed at baseline, week 4, week 8 and follow up and takes about 20 minutes to complete. This scale is completed by the parent and is meant to show the burden to the caregiver and the family by the disorder being studied, in this case, PWS.

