The time commitment and study burden is similar to other current studies in this population and the ASD population. If needed, visits can be split into two visits. Parents may prefer to attend a visit by themselves without the child to complete their measures. Visits at screening, weeks 2, 4, 6, and 10 (follow-up) are remote visits done via tele-medicine. The study clinicians will complete the video conference call with the parent. This will further reduce the family's burden and decrease the amount of times they need to travel to the study site. As much flexibility in scheduling as necessary will be given to the patients and families. Reimbursement for time and travel is provided at each visit (\$150 – in-person; \$30 – phone visit). Additional reimbursement for travel will be provided as needed for families traveling long distances. The average time needed for parents, child and clinician to complete the assessments is detailed below. Details about which measures are included in each visit can be seen in **Table 2: Schedule of Events.** Some assessments require the participation of both the parent and child and times reflect how long each individual is needed independent of combined measures. Families may differ in how long it takes them to complete certain measures and the times do not include any breaks for meals or walking between sites at the clinic.

Screening Visit (remote): 3-4 hours Baseline Visit (in-person): 4-5 hours Week 2 and Week 6 (remote): 30 minutes Week 4 (remote): 2-3 hours Week 8 (in-person): 4-5 hours Week 10 Follow Up (remote): 2-3 hours

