Psychiatric Interview	30 min	Parent/Child/Cli nician	х						
Intelligence Test	60 min	Clinician/ Child		Х					
Randomization	0 min			Х					
Concomitant Medications	5 min	Parent/Child/Cli nician	х	х	х	x	х	х	Х
Adverse Events/Monitoring for hypogonadism, sleep apnea, lethargy	10 min	Parent/Child/Cli nician	x	х	x	x	x	х	x
Standard Laboratory Tests*	10 min	Clinician/ Child	X***	Х				Х	
Hormone and Metabolic Laboratory Tests**	10 min	Clinician/ Child		х				х	
Treatment Given	10 min	Parent/Child/Cli nician		х		x		х	
Urine Pregnancy Test (if appropriate)	5 min	Child/Clinician	х	Х				х	
Vital signs	15 min	Clinician/ Child		Х				Х	
Eating Behavior Measures									
Hyperphagia Questionnaire- Clinical Trials (HQ-CT)	15 min	Parent/Child/Cli nician	х	х	x	x	х	x	х
Weight, Body Composition and BMI	5 min	Parent/Child/Cli nician		х				х	
Dietary Diary ASA24 Automated Self-	15 min	Parent		х				х	

Administered 24 Hour Recall									
Repetitive Behavior Measures									
Montefiore-Einstein Rigidity Scale –Revised (MERS-PWS)	15 min	Clinician		х		х		x	х
RBS-R	15 min	Parent		X [pre-dose]		х		x	х
Oxytocin Measures									
Salivary Oxytocin Levels	10 min	Clinician/Child		X [pre- and 1 hour post dose]		X [pre- and 1 hour post dose]		X [pre- and 1 hour post dose]	x
Global Clinical Improvement and Quality of Life Measures									
ABC-I (Full ABC will be completed to measure this subscale)	25 min	Parent		X [pre-dose]	х	х	х	x	х
CGI-I	5 min	Clinician			X	Х	Х	Х	Х
CGI-S	5 min	Clinician	Х	Х					
WHOQOL	20 min	Parent/Child/ Clinician		Х		х		x	х
Caregiver Strain Questionnaire	10 min	Parent		Х		Х		Х	х

\* Standard Laboratory Tests: CBC, CMP including sodium, IGF-1, thyroid panel, lipid panel, hemoglobin A1C, and urine pregnancy test
 \*\* Hormone and Metabolic Laboratory Tests: testosterone, estrogen, growth hormone, ghrelin, pancreatic polypeptide, peptide YY, leptin, GLP-1, insulin, glucagon

\*\*\* To be done at local Quest

Table 2: Intranasal Oxytocin vs. Placebo for the Treatment of Hyperphagia in Prader-Willi Syndrome SCHEDULE OF EVENTS

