*Predicted Enrollment:* We expect that the Foundation of Prader-Willi Research (FPWR) and their Global PWS Registry to be the greatest source of recruitment for our study. There are over **700** patients interested in participating in research that we will have access to with their Clinical Trials Alert newsletter. Additionally, the Global PWS Registry will collect data that will allow us to pre-screen patients based on our inclusion/exclusion criteria. Through [name] center we will have access to over **450** patients. [name] practice has over **300** patients with PWS. We have budgeted significant funding to provide travel reimbursement to patients that will need to travel long distances to our center and do not expect that to play an issue in the recruitment and enrollment for our study due to the enthusiasm of this population for clinical research. In total we will thus have access to, at minimum, **1450** patients and families affected by Prader-Willi Syndrome. Even if we use an elevated pre-screening/screen failure rate of 80%, to account for patients that are not interested, do not meet I/E criteria, or who do not wish to travel to our site, we would still have access to approximately **300** patients that would be study eligible.

As mentioned above, we are already in contact with 40 families/patients that are interested in research and meet the criteria for this study. Study subjects will be drawn from the resources above and referrals, as well as from the diverse and large clinical practice of the PI, [name]. Additional recruitment methods include advertisements in local media, referrals from patients' personal physicians and the clinical affiliations of the PI and collaborators. Prescreening/screening procedures are detailed below. Study visits have been kept to the safest minimum to reduce caregiver burden and travel time. Reimbursement of \$150 for each inperson visit (2 visits) and \$30 for each remote visit (5 visits) will be provided, for a total of \$450 over the course of the study. This reimbursement covers compensation for time and reimbursement for travel expenses to the site. Additional funds have been allocated to provide for long-distance travel for patients outside of the tri-state area.

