  - *b.* The effects of treatment on frequency and severity of repetitive behaviors will be assessed by fitting linear mixed effects models to the data on the MERS-PWS scores. We hypothesize that IN- OXT will significantly reduce repetitive behaviors from baseline to endpoint compared to Placebo.
- 2. Secondary Aim (2) Weight, BMI (z-score) and body composition via bioelectrical impedance analysis
  - a. Weight and BMI (z-score) will be measured at each visit. It will be utilized to evaluate whether IN-OXT significantly modulates energy metabolism and reduces weight compared to placebo. Body composition via impedance analysis will be measured at baseline and endpoint.
- 3. Secondary Aim (3) Quality of Life Measures
  - a. The relationship between quality of life and treatment will be assessed using scores on the WHOQOL. We hypothesize that IN-OXT will improve quality of life from baseline to endpoint as measured by an increase in overall score on the WHOQOL from when compared to placebo.
  - b. The relationship between caregiver strain and treatment will be assessed using scores on the CSQ. We hypothesize that IN-OXT will caregiver strain from baseline to endpoint as measured by an reduction in overall score on the WHOQOL from when compared to placebo.
- 4. Secondary Aim (4) Salivary Oxytocin Levels
  - a. Both group and individual differences in salivary OXT concentration will be measured. Correlations between individual salivary OXT concentrations at day 1 and weeks 4 and 8 as well as correlations between OXT and changes in our primary outcome measure, hyperphagia assessed by the [name] Hyperphagia Questionnaire, will be evaluated using the Spearman rank or Pearson correlation. Additional correlation analysis will be performed on salivary oxytocin levels and secondary outcome measures: RBS-R, WHOQOL and CGI-I. We hypothesize that higher concentrations of salivary oxytocin will be correlated with positive changes on each outcome measure, indicating improvement in symptoms.
- 5. Secondary Aim (5) Safety Analyses
  - a. Rates of specific side effects and other adverse events will be tabulated and compared between treatment groups using the chi-square test. Please see the section labeled "Safety Analyses" for further details on how adverse events will be monitored and rated.

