**Risks:**\_Studies have shown risks of IN-OXT to be minimal with no difference in AE burden between IN-OXT and placebo [46]. The most common categories of side-effects seen include:

- increased calmness/euphoria or more energy
- light headedness
- drowsiness/fatigue
- headache
- nasal irritation
- dry mouth/throat

As noted above, one study of IN-OXT in PWS noted increased levels of aggression, via temper tantrums, at higher doses of IN-OXT. As very few studies have reported on the extended use of IN-OXT there may be other unknown side effects, although our 6-week studies showed no difference in AEs. Other risks relate to venipuncture procedures for blood sampling taken at key points in the study as a safety measure. Blood draws and anthropometric measures will be completed at the CTSA sponsored Clinical Research Center (CRC), which has trained nursing and lab staff. In addition, patients may feel uncomfortable answering some of the questions presented during the assessments and breaks will be provided if needed. There is a risk of loss of confidentiality, although every step is being taken to keep patient files and data secure. All data is locked in staff offices or on staff computers and only authorized personnel or organizations indicated in the consent (IRB; FDA etc.) will have access. Pediatric neurologist [name], PhD is the independent medical monitor and will review side effects after each study visit to ensure subject safety and to determine if a subject's participation should be terminated due to an AE.

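### The text calls for weight and BMI z-score at every visit, but Table 2 schedules them, with body composition, only at baseline and week 8; the text should match the table and name one baseline-adjusted week-8 analysis

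*Combined protocol and SAP*

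**What the plan says.** Four parts of the combined protocol and SAP bear on when these outcomes are measured.

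- **Secondary Outcome Measures, Weight, BMI (z-score) and Body Composition:** "Weight and BMI (z-score) will be measured at each visit using a regularly calibrated scale", and "Body composition, in particular fat mass, will also be measured at each visit using bioelectrical impedance analysis".
- **Detailed Description of Analyses, Secondary Aim (2):** "Weight and BMI (z-score) will be measured at each visit", but "Body composition via impedance analysis will be measured at baseline and endpoint".
- **Table 2, Schedule of Events:** a single row, "Weight, Body Composition and BMI", is marked at baseline and week 8 and is blank at screening and weeks 2, 4, 6 and 10. The Outcome Measures paragraph says that assessments follow this table.
- **Study Time Commitment and Reduction of Burden:** "Visits at screening, weeks 2, 4, 6, and 10 (follow-up) are remote visits done via tele-medicine".

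The Risks paragraph places anthropometric measures at the Clinical Research Center. No section describes weighing or impedance measurement at home.

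On analysis, the Specific Aims define the secondary endpoints as change from baseline to week 8. The Summary of Analytic Approach offers several routes: an unadjusted comparison at a given time point; a comparison of change, or ANCOVA if an exploratory look suggests that change depends on baseline; and mixed models on all repeated follow-up measurements. Secondary measures are to be handled by methods similar to those for the primary outcome.

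**The concern.** The outcome and analysis sections give a measurement rule that the visit structure cannot deliver, and they disagree with each other on body composition. Weight, BMI and body fat carry named secondary hypotheses, and the outcome section treats weight and fat as markers of efficacy. A reader of the text would expect a repeated-measures series; a reader of Table 2 would expect a baseline and one follow-up value. The two expectations imply different data sets and different models, and the analysis section does not say which model decides these outcomes. At stake is the clarity of a secondary analysis: whether a trajectory was planned, whether blank remote visits count as missing data, and which of several tests is the reported one.

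**Working it through.** **Sample-size figure.** The Power Analysis gives 80% power with 25 per arm, d = 0.8 and two-sided alpha 0.05. The normal approximation is Φ(d√(n/2) − 1.96) = Φ(0.8 × √12.5 − 1.96) = Φ(0.868) = 0.807; the noncentral t gives 0.791. The figure reproduces. It is not specific to weight and does not depend on the number of weight measurements.

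**Visit count.** The visits are screening, baseline and weeks 2, 4, 6, 8 and 10, which makes 7. Baseline and week 8 are in person (2) and the rest are remote (5). The reimbursement total in the Recruitment section agrees: 2 × $150 + 5 × $30 = $450.

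**Timing by source.**

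| Source | Weight, BMI z-score | Body composition |
|---|---|---|
| Secondary Outcome Measures | each visit | each visit |
| Secondary Aim (2), analysis text | each visit | baseline and endpoint |
| Table 2 | baseline, week 8 | baseline, week 8 |

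The HQ-CT row of the same table is marked at all seven visits, so the blanks in the weight row do not look like an extraction fault.

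**Size of the gap for weight and BMI.**

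- Visits with no scheduled or described measurement: 5/7 = 71%.
- Assessments for 50 subjects: 50 × 7 = 350 under the text and 50 × 2 = 100 under Table 2, a difference of 250.
- Post-baseline values per child: 5 under the text (weeks 2, 4, 6, 8, 10) and 1 under Table 2 (week 8).

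**Consequence for the mixed model.** The planned model has time, treatment and their interaction. With follow-up values only, Table 2 supplies one time point, so neither a time effect nor an interaction can be estimated. If baseline is entered as a response there are two time points, and with complete data the interaction estimate is simply the between-arm difference in mean change. Either way the model adds little to a direct week-8 comparison.

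**Why one adjusted analysis is better.** Assume equal variance σ² at baseline and week 8, and correlation ρ between them. The relevant variances are:

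- week-8 value alone: σ²
- change: 2σ²(1 − ρ)
- ANCOVA residual: σ²(1 − ρ²)

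Since 2(1 − ρ) − (1 − ρ²) = (1 − ρ)² ≥ 0, ANCOVA is never less precise than change, and it is never less precise than the week-8 value alone, apart from the one degree of freedom spent on the covariate. The documents give no ρ for these outcomes. In children aged 5 to 17, however, body weight at a single visit mostly reflects age and size, so the unadjusted week-8 test is a poor choice for weight in particular. ANCOVA is at least as good at any ρ, so nothing is gained by letting the data choose between it and the change test.

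**The case against.** The best reply is that the protocol already settles the matter. It says that assessments follow Table 2, and it sends the reader to that table again when describing the visits. On that view the each-visit wording is most plausibly left over from before telemedicine visits were introduced, although that is an inference. The endpoint is the baseline-to-week-8 change, both measurements are scheduled in person, and no stated weight hypothesis needs the weeks between. Mixed models are named specifically for the RBS-R and MERS-PWS and reach weight only through a general clause. All of this stands, and it limits the point to a contradiction to be reconciled.

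A reader might infer something stronger in two ways.

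- **That the weight endpoint cannot be collected.** The documents do not support this, because baseline and week 8 are both clinic visits with the row marked.
- **That remote values from family scales would enter the model and bias it.** No section mentions home scales or caregiver-reported weights. The outcome section requires a calibrated scale, so an uncalibrated home weight would breach it. The Special Circumstances section allows other locations only in general terms. Even if such values were recorded, the visit pattern is the same in both randomized arms and the clinic-measured week-8 contrast would be untouched.

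The reply does not remove two things: operative text in two sections that cannot be carried out, and an analysis section that leaves open which test applies to these outcomes.

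**Conclusion.** The contradiction holds. The text asks for weight and BMI z-score at seven visits, while the governing schedule provides two; for body composition the two text sections also disagree with each other. Five of seven visits have no described means of measurement, so the repeated-measures model has one post-baseline value where the text implies five. The baseline-to-week-8 comparison keeps both its time points, the stated power is unaffected, and no bias in the week-8 contrast is shown. This should be corrected, but it does not threaten the endpoint. The conclusion assumes that Table 2 governs, as the Outcome Measures paragraph says, and that no remote measurement procedure exists outside these documents.

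**What to change.** Amend the weight and body-composition section and Secondary Aim (2) to match Table 2: weight, BMI z-score and impedance body composition at the in-person baseline and week-8 visits, on the same calibrated equipment at both. State that each of these outcomes is compared between arms by ANCOVA, with the week-8 value as outcome and treatment and baseline value as terms. For these outcomes this replaces the unadjusted week-8 test, the choice between a change test and ANCOVA made after looking at the data, and the mixed model.

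The cost is a few sentences in two sections and one in the analysis plan. The small downside is that the text gives up an intermediate weight trajectory, which the remote design does not provide in any case. If the sponsor wants that trajectory, the alternative is a specified, standardized remote procedure added to Table 2, at greater cost.

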#### Caregiver Strain Questionnaire (CSQ):

The Caregiver Strain Questionnaire is a well-validated, reliable 21-item measure of selfreported strain experienced by caregivers and families of youth with emotional problems, with responses on a 5-point Likert scale (0 = Not at all, 4 = very much).

**Clinical Global Impression Scale – Improvement (CGI-I):** The CGI-I will be used as a measure of improvement and contains a 7 point scale as follows: 1 = very much improved, 2 = much improved, 3 = minimally improved, 4 = no change, 5 = minimally worse, 6 = much worse, 7 = very much worse. The CGI-I has been used as a measure in previous clinical psychopharmacology trials and will be completed by the study physician and clinician at each visit based upon clinical observations. It is a clinician rated global measure of improvement that will be completed at baseline, weeks 2 through 8 and at follow-up. It takes about 5 minutes.

**Salivary Oxytocin Levels:** Saliva will be collected by means of an Oragene-Discover collection kit (ORG-500). If able, subjects will spit saliva directly into the collection tube. If the child is unable to spit into the tube, we will use Oragene's OG-AC1 assisted collection swabs to collect saliva from the inside subject's cheeks. Samples will be collected pre-dose and one-hour post-dose at baseline, week 4 and week 8. A salivary sample will also be taken at the follow up visit. It takes approximately 10 minutes to complete.

*Justification for Measurement of Salivary Levels:* We have selected salivary measures of OXT, since Gordon et al [73] demonstrated that salivary OXT levels are directly correlated with brain activity and enhancements in brain function. After administration of IN-OXT, levels of salivary OXT increase markedly and have been shown to remain elevated for up to 7 hours after administration vs. placebo. In fact, low doses (16 IU OXT) did not show weaker effects and tended to elevate the initial salivary OXT compared to higher doses (24 IU). Salivary OXT levels on placebo were highly correlated over time, indicating individual stability of OXT levels. Another study [100], utilized a double-blind placebo-control within-subject design. Ten subjects

were administered IN- OXT or placebo and salivary OXT was measured ten times over four consecutive hours. IN-OXT increased salivary OXT across the entire period. OXT rose dramatically 15 min after administration (from 6.9 pg/ml at baseline to 1265.4 pg/ml), reached plateau at 45—120 min (range = 131.6 and 105.3 pg/ml), and did not return to baseline by 4 h. The findings from these studies support target engagement in the CNS and refute the idea that salivary elevation results solely from movement of mucus from the nasal cavities back into the mouth.

We believe that plasma OXT levels are of less importance, as central and clinical effects do not reflect plasma PK levels, but that salivary OXT levels may be more closely correlated with CNS effects. We do not expect our one hour post-dose measurements to be affected by IN-OXT residue in the nasal cavity. As stated above, Gordon et al. [73] demonstrated salivary levels of OXT 30 minutes post-dose were strongly correlated with changes in brain activity and van IJzendoorn et al [99] demonstrated that salivary OXT levels peak 1 hour post- dose and a dose of 16 IU was correlated with higher salivary OXT levels than a 24 IU dose. Salivary concentrations are being measured at weeks 4 and 8 to determine if salivary OXT concentrations accumulate over time with chronic treatment of IN-OXT and to determine if the levels correlate with changes in clinical symptoms. We will measure both group and individual differences in salivary OXT concentration in addition to correlating individual salivary OXT concentrations at day 1 and weeks 4 and 8 with changes on the [name] Hyperphagia Questionnaire. We also believe that salivary OXT concentration measurements will induce less discomfort than plasma measurement for the children enrolled in the study. In sum, while levels of salivary oxytocin remain elevated for up to 7 hours, the standard and maximum levels observed in prior studies was observed at the 1 hour post-treatment measurement.

**IQ Test: Stanford-Binet Intelligence Scales, Fifth Edition:** The Stanford-Binet will be administered to obtain data on adaptive behavior and intellectual functioning for correlation during analyses. It is a gold standard measure of intelligence used in clinical and research settings in those aged 2 to 85 years. The fifth edition has a 50/50 balance between verbal and nonverbal subtests, and the Stanford-Binet is considered the best assessment of intelligence in those with intellectual disability and mental retardation 12. Administration time is approximately 5 minutes per subtest.

**Dietary Assessment:** Dietary intake will be assessed using the National Cancer Institute (NCI) 24-hour automated recall method, which will be completed by the primary caregiver in 15 to 20 minutes. Three dietary recalls (randomly assigned days to include two weekdays and one weekend day) will be obtained to assess pre-treatment dietary habits at baseline and repeated at endpoint. The NCI nutritional program output will allow for secondary analyses of impact of treatment on both dietary macronutrient ratio (percent carbohydrates, proteins and fats) and caloric intake.

